| Diagnosis and Main Inclusion Criteria | 
Main Inclusion Criteria:
 
 • Histopathologically confirmed diagnosis of metastatic advanced cutaneous squamous cell carcinoma. • History of solid-organ transplant requiring immunosuppression • Age ≥ 18 yrs • Measurable disease by RECIST v1.1 • KPS $\geq 60\%$, ECOG ≤ 2 • No prior JAK Inhibitor therapy • Adequate organ function • All clinically significant toxicities from prior systemic therapy must be \leq Grade 1 (with the exception of alopecia, and peripheral neuropathy, which may be \leq grade 2). • Subjects must agree to undergo tumor biopsies until biopsies have been obtained from 10 subjects (i.e., biopsies are required in at least the first 10 enrolled subjects, or until a goal of 10 study biopsies are obtained). Subjects in whom a biopsy is technically not feasible or in whom would result in unacceptable risk in the opinion of the investigator, may be exempted from the biopsy requirement with discussion with the principal investigator. • Negative pregnancy test for women of child bearing potential • Ability to take oral medications • Adequate marrow function: 
 - ANC ≥ 1000 /mm³ - Platelet count $\geq 50,000$/mm³ - Hemoglobin ≥ 8.0g/dL (not requiring transfusion in the past 2 weeks) |
| Study Product, Dose, Route, Regimen | Ruxolitinib will be administered orally twice daily during the entirety of each 28-day cycle. There will be a safety lead-in cohort of 6 patients who receive the starting dose of 15mg twice daily (BID). If dose limiting toxicities (DLT) are seen in 1 or fewer patients, the starting dose for all remaining patients will be 15mg BID. If DLT's are seen in >1 patient, another 6 patients will be enrolled at 10mg BID. If DLT's are seen in 1 or fewer patients, the starting dose for the remaining patients will be 10mg BID. Otherwise the study will be terminated. Individual subjects may have dose reductions of ruxolitinib during the course of treatment, based upon safety laboratory assessments. |

| | |
|-----------------------------------|---|
| Duration of administration | Treatment with ruxolitinib will commence following enrollment and continue until objective disease progression as confirmed by RECIST v1.1, intolerable toxicity or the occurrence of another discontinuation criterion. |

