5. STUDY DESIGN

5.1 General Design

This is an open-label, multi-center, Phase II study to evaluate the efficacy of ruxolitinib in post-transplant patients with advanced cutaneous squamous cell carcinoma.

Study Intervention: In a safety lead-in of 6 patients, subjects will receive ruxolitinib 15mg BID. After 4 weeks, if dose-limiting toxicities (DLT) are observed in 1 or fewer patients, the study will enter stage 1 of the Simon two-stage design where all subsequent patients will receive a starting dose of ruxolitinib 15mg BID. If more than 1 DLTs are observed, another cohort of 6 patients will be treated at a dose of 10mg BID. If less than 2 DLTs are observed at the new dose of 10mg, then the study will proceed to stage I using this dose; otherwise the study will stop.

Individual subjects may have dose reductions of ruxolitinib during the course of treatment, based upon safety laboratory assessments.

Schedule of Evaluations: Subjects will have regularly scheduled study visits at the clinical site on Day 1 and Day 15 (\pm 3 days) of the first cycle, then on Day 1 (\pm 3 days) of every subsequent cycle (starting cycle 2), where safety assessments, including laboratory assessments, vital signs, and physical examinations will be performed (see Section 12 for study calendar).

Response to treatment will be determined by CT scans of the chest, abdomen, and pelvis with contrast. The overall response rate for the primary endpoint evaluation will be determined by RECIST v1.1 criteria. In patients who are unable to get a CT scan w/ contrast due to renal function (or any other reason), an MRI with and without contrast may be used instead. Imaging will be performed at the following time points:

| | |
|--------------------------------------|---|
| Baseline scan | Baseline scan within 4 weeks prior to first treatment |
| Weeks 1 – 32 | Every 8 weeks +/- 1 week (at weeks 8, 16, 24, 32) |
| Weeks 33 – until disease progression | Every 12 weeks +/- 1 week (at weeks 44, 56, 68, 80, 92, 104) |
| 2 years | If subjects achieve ongoing disease control at 2 years, patients will be continued on study treatment and observed with imaging every 12 weeks +/- 2 weeks. |

Duration of treatment: Subjects will continue treatment until confirmed radiographic disease progression, intolerable toxicity or side effects (Section 6.5.1).

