6. SUBJECT SELECTION AND WITHDRAWAL

6.1 Inclusion Criteria

1. Histologically confirmed diagnosis of cSCC.
2. Unresectable or metastatic cSCC.
3. History of solid-organ transplant requiring immunosuppression
4. Allowable prior therapies:
 - a. A maximum of 4 prior therapies for metastatic disease are allowed.
5. Male or female subjects, age 18 years or older.
6. ECOG performance status ≤ 2 (Appendix A)
7. Life expectancy of ≥ 3 months.
8. Laboratory parameters within the following Protocol-defined range. All screening laboratory tests should be performed within 28 days of treatment initiation and must be independent of hematopoietic growth factor support.
 - Absolute neutrophil count $\geq 1.5 \times 10^9/L$.
 - Platelets $\geq 100 \times 10^9/L$.
 - Hemoglobin $\geq 9 \text{ g/dL}$ (transfusion is acceptable to meet this criteria)
 - Serum creatinine $\leq 1.5 \times$ institutional upper limit of normal (ULN) OR calculated creatinine clearance $\geq 50 \text{ mL/min}$ for subjects with creatinine levels $> 1.5 \times$ institutional ULN.
 - Aspartate aminotransferase, alanine aminotransferase, alkaline phosphatase $\leq 2.5 \times$ ULN, or $\leq 5 \times$ ULN in subjects with liver metastases.
 - Total bilirubin $\leq 1.5 \times$ ULN
 - **Note:** patients with hyperbilirubinemia clinically consistent with an inherited

disorder of bilirubin metabolism (eg, Gilbert syndrome) will be eligible at the discretion of the principal investigator.

- International normalized ratio (INR) or prothrombin time (PT) $< 1.5 \times$ ULN unless subject is receiving anticoagulation therapy as long as PT or INR is within therapeutic range of intended use of anticoagulant.
- Activated partial thromboplastin time (aPTT) $< 1.5 \times$ ULN unless subject is receiving anticoagulant therapy, as long as PTT is within therapeutic range of intended use of anticoagulants.

9. Presence of baseline measureable disease by RECIST v1.1 for solid tumors, defined as at least one lesion that can be accurately measured in at least one dimension (longest diameter to be recorded for non-nodal lesions and short axis for nodal lesions) as ≥ 20 mm with conventional techniques or as ≥ 10 mm with spiral CT scan, MRI, or calipers by clinical exam. (See Section 15.4 for the evaluation of measurable disease).

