Serious bacterial, mycobacterial, fungal, viral and other opportunistic infections have occurred in patients treated with ruxolitinib. Patients should be assessed for the risk of developing serious infections. Physicians should carefully observe patients receiving ruxolitinib for signs and symptoms of infections and initiate appropriate treatment promptly. Ruxolitinib therapy should not be started until active serious infections have resolved.

Hepatitis B viral load (HBV-DNA titer) increases, with and without associated elevations in ALT and AST, have been reported in patients with chronic HBV infections taking ruxolitinib. The effect of ruxolitinib on viral replication in patients with chronic HBV infection is unknown. Patients with chronic HBV infection should be treated and monitored according to clinical guidelines.

Tuberculosis

TB has been reported in patients receiving ruxolitinib for MF. Before starting ruxolitinib therapy, patients should be evaluated for latent or active TB as per local recommendations. This can include medical history, possible previous contact with TB, and/or appropriate screening such as lung x-ray, tuberculin test and/or interferon-gamma release assay, as applicable.

Physicians are reminded of the risk of false negative tuberculin skin test results, especially in patients who are severely ill or immunocompromised.

Withdrawal effects

Following interruption or discontinuation of ruxolitinib, symptoms of MF may return over a period of approximately one week. There have been cases reported of patients discontinuing ruxolitinib who sustained more severe events, particularly in the presence of acute intercurrent illness.

Hepatic impairment

In patients with any hepatic impairment the recommended starting dose based on platelet count should be reduced by approximately 50% (or as specified in country specific product labels).

Patients diagnosed with hepatic impairment while receiving ruxolitinib should be carefully monitored and may need to have their dose reduced to avoid ADRs.

Dose adjustment with concomitant CYP3A4 inhibitors/inducers/substrates

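### Section 10.1 advises about half the starting dose in hepatic impairment, but the sections that set the starting dose make no hepatic exception

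*Combined protocol and SAP*

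**What the plan says.** Among its warnings and precautions, Section 10.1 has a short paragraph on hepatic impairment. It opens "In patients with any hepatic impairment" and continues that in "hepatic impairment the recommended starting dose based on platelet count should be reduced by approximately 50% (or as specified in country specific product labels"). A second sentence deals separately with "Patients diagnosed with hepatic impairment while receiving ruxolitinib", who are to be monitored and may need a lower dose. The first sentence is therefore about the dose at the start and the second about changes later.

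The starting dose itself is set elsewhere:

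- **Synopsis, dosing row.** "There will be a safety lead-in cohort of 6 patients who receive the starting dose of 15mg twice daily (BID"). If the lead-in passes, "the starting dose for all remaining patients will be 15mg BID". If it fails, a second six are treated at 10mg BID, and that becomes the starting dose if they pass.
- **5.1 General Design.** The same scheme, ending in stage 1 "where all subsequent patients will receive a starting dose of ruxolitinib 15mg BID". It adds: "Individual subjects may have dose reductions of ruxolitinib during the course of treatment, based upon safety laboratory assessments".
- **11.2 Treatment Regimen.** A start of 10mg twice daily, conditional only on blood counts.
- **8.1 and Section 9.** 8.1 refers the site to Section 9 for dose modifications. Section 9 gives criteria for beginning a cycle, a ladder of dose levels (Table 1) and toxicity tables (Tables 2 to 6). It has no starting rule for liver function and no liver-specific row.

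On eligibility, 6.1 limits AST, ALT and alkaline phosphatase to 2.5 x ULN (5 x ULN with liver metastases) and bilirubin to 1.5 x ULN, with an exception for inherited bilirubin disorders. It requires INR/PT and aPTT below 1.5 x ULN unless the patient is anticoagulated. 6.2 excludes active hepatitis B or C and chronic hepatitis needing antivirals. The transplant criterion, "History of solid-organ transplant requiring immunosuppression", does not restrict the organ.

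**The concern.** One part of the protocol says that a patient with any hepatic impairment should start at about half the dose. The parts that a site would follow when writing the first prescription give that patient the full cohort dose. No section defines hepatic impairment for dosing, so the site has nothing with which to settle the conflict.

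What is at stake is the first-cycle dose of a drug that 10.1 says causes more myelosuppression when repeat doses exceed those recommended. The sample size, the response endpoint and the two-stage error rates do not depend on this point.

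**Working it through.** The plan states no figure to reproduce here. The check compares the texts and then sizes the gap.

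**1. Is there a hepatic branch anywhere in the starting-dose rules?** No. In the synopsis and 5.1 only lead-in DLTs decide between 15 and 10mg BID. In 11.2 only blood counts matter. The laboratory-based reductions in 5.1 apply after treatment has begun. The discretion clause in 9.2 covers adverse events that its tables omit, not a patient's condition at baseline.

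**2. Can a patient to whom 10.1 applies be enrolled?** Yes, within limits. The 6.1 limits decide entry and are not tied to dose. Abnormal tests are not in themselves hepatic impairment, but 10.1 covers impairment of any degree, and 6.1 admits raised enzymes and mildly raised bilirubin. The documents do not say how many such patients to expect.

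**3. How large is the gap?** Inputs are the cohort doses (synopsis, 5.1) and the reduction of about 50% (10.1). The advice is taken to apply to the trial's own starting dose, because this trial has no platelet-based one.

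- Cohort dose 15mg BID: 15 x 2 = 30mg/day. Half is 15mg/day. Ratio 30/15 = 2.0.
- Cohort dose 10mg BID: 10 x 2 = 20mg/day. Half is 10mg/day. Ratio 20/10 = 2.0.

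Sensitivity to that assumption: 4.5 reports platelet-based starts of 20 or 15mg BID in a cited placebo-controlled myelofibrosis trial. Halving those gives 20 or 15mg/day. Against a 15mg BID start the ratio is then 30/20 = 1.5 to 30/15 = 2.0. Against a 10mg BID start it is 20/20 = 1.0 to 20/15 = 1.33. Nothing in the documents says that scheme applies here, so twofold is an upper figure. The label alternative in 10.1 could also change it.

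**4. Which existing dose level could serve?** From Table 1:

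| Candidate start | mg/day | Cut from 15mg BID (30mg/day) | Cut from 10mg BID (20mg/day) |
|---|---|---|---|
| 10mg BID (level 0) | 20 | 1 - 20/30 = 33% | none |
| 5mg BID (level -1) | 10 | 1 - 10/30 = 67% | 1 - 10/20 = 50% |

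No Table 1 level is exactly half of 15mg BID. A split of 10mg plus 5mg daily is exactly half (15mg/day) and can be made from the 5mg tablets in 11.6, but it is not a Table 1 level. 5mg BID is the highest existing level that gives at least a 50% reduction from either cohort dose. It leaves one lower level, 5mg once daily. The limit of two reductions in Section 9 is a cap, so this start does not breach it.

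**The case against.** The strongest reply is that the 10.1 sentence is product text carried over without tailoring. It adjusts a platelet-based dose that this trial does not use, the surrounding paragraphs discuss the return of myelofibrosis symptoms, and 8.1 assigns adverse events and risks to Section 10 and dose changes to Section 9. On that view there is one dosing rule and some background. The description of the text is fair, but it does not remove the conflict. The sentence recommends a starting dose in a protocol that sites must follow, and nothing says that it does not govern.

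A second reply is that eligibility already deals with the problem. It largely does for marked impairment, and that part stands: few patients may be affected. A third is that the label alternative may resolve the dose. That also stands, which is why the twofold figure is conditional.

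Three stronger readings should be resisted.

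- A reader might infer that nothing says whether a reduced-start patient counts in the lead-in. The synopsis and 5.1 describe those six as patients receiving 15mg BID, so the answer is already implied.
- A reader might infer that reduced starts would materially distort the chance of passing the lead-in. Putting a number on that needs DLT rates that the documents do not give, and an assumption that the reduced-start patient carries no DLT risk. If that patient's risk equals the others', the chance does not change.
- A reader might infer a twofold spread between sites that do reduce. That appears only if the rounding rule written for strong CYP3A4 inhibitors is borrowed, and the split dose of 10mg plus 5mg shows that half is attainable.

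**Conclusion.** The inconsistency is real and limited. The protocol advises about half the starting dose in any hepatic impairment, while its operative dosing sections give every patient the cohort dose. An eligible patient with hepatic impairment could start at up to about 2.0 times the dose 10.1 recommends. This assumes that the advice applies to the trial's own starting dose and that the product label does not say otherwise. The documents do not give the number of such patients, and the limits in 6.1 and 6.2 suggest it is small.

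The point should not be read as saying that 6.1 lacks liver limits. It has them, but they decide entry and not dose. This is a dosing-safety matter that deserves correction by amendment, and it is no threat to the primary analysis.

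**What to change.** 1. Check the product label that 10.1 points to and take from it the threshold for hepatic impairment.
2. Add one exception to the synopsis, 5.1 and 11.2: a patient who meets that threshold at screening starts at 5mg BID (Table 1 level -1), whichever cohort dose is in force.
3. State that such patients are not enrolled among the six lead-in patients, which makes explicit what the synopsis and 5.1 imply.
4. In 10.1, replace the reference to a platelet-based dose with a reference to this rule.

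The cost is amendment wording. Liver function tests are already on the screening calendars in 13.1 and 13.2, though the label should be checked for any item that they do not cover. No new dose level is needed. The downside is that a few patients start lower than they do now: 67% below 15mg BID, which is more than the half that 10.1 advises, or 50% below 10mg BID. They would also have only one further reduction available. Under 17.2 they stay in the efficacy and safety analyses, so the sample size does not change.

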6.2 Exclusion Criteria

1. At least 21 days must have elapsed since the last dose of systemic chemotherapy or immunotherapy and the first dose of study drug.
2. At least 14 days must have elapsed since the last dose of radiation therapy and the first dose of study drug.
3. Patients who have previously been treated with a JAK inhibitor.

4. Patients who are receiving any other investigational agents concurrently.
5. Patients who have had recent major surgery within a minimum 4 weeks prior to starting study treatment, with the exception of surgical placement for vascular access.
7. Patients with a history of allergic reactions attributed to compounds of similar chemical or biologic composition to ruxolitinib.
8. Patients with symptomatic or growing brain metastases. Patients with brain metastases that have been treated and have remained stable for at least one month prior to initiation of study therapy are eligible.
9. Concurrent use of strong CYP3A4 or CYP3A4 substrate drugs with a narrow therapeutic range within 14 days or 5 drug half-lives, whichever is longer, before start of study drug. A list of strong CYP3A4 and 2C8 inhibitors and inducers can be found in Appendix C.
10. HIV-positive patients on combination antiretroviral therapy are ineligible because of the potential for pharmacokinetic interactions with ruxolitinib. In addition, these patients are at increased risk of lethal infections when treated with marrow-suppressive therapy.
11. Subjects with known active hepatitis B or C, or chronic hepatitis B or C requiring treatment with antiviral therapy.
12. Uncontrolled intercurrent illness including, but not limited to, ongoing or active infection, symptomatic congestive heart failure, unstable angina pectoris, cardiac arrhythmia, or psychiatric illness/social situations that would limit compliance with study requirements.
13. Patients being actively treated for a second malignancy.

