8. TREATMENT PLAN

8.1 Agent Administration

Treatment will be administered on an outpatient basis. Reported adverse events and potential risks for ruxolitinib are described in Section 10. Appropriate dose modifications for ruxolitinib are described in Section 9. No investigational or commercial agents or therapies other than those described below may be administered with the intent to treat the patient's malignancy.

If all eligibility criteria are met, study participants will initiate ruxolitinib twice daily. One cycle will consist of 4 weeks of therapy.

- Patients will be provided with a Medication Diary for ruxolitinib (Appendix D), instructed in its use, and asked to bring the diary with them to each appointment.
- Doses of ruxolitinib will be taken orally with approximately 8 oz. of water. Subjects should fast at least 1 hour before administration and 1 hour after administration

of the drug. Study drug should be taken at approximately the same time each day. Study drug should be swallowed whole and not crushed, chewed, or dissolved in water.

- Missed doses (outside of a 2 hour dosing window) should be skipped and not administered as a double dose at the next administration. Missed doses should be recorded on the Medication Diary but will not be considered violations of the protocol.
- Subjects who vomit their dose should be instructed NOT to make up that dose. Doses that are vomited should not be replaced.
- Patients will be instructed that ruxolitinib can be stored at room temperature.
- No premedication or other supportive medications are required.

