When ruxolitinib is administered with strong CYP3A4 inhibitors (such as, but not limited to, boceprevir, clarithromycin, indinavir, itraconazole, ketoconazole, lopinavir/ritonavir, ritonavir, mibefradil, nefazodone, nefazodone, nelfinavir, posaconazole, saquinavir, telaprevir, telithromycin, voriconazole) as well as fluconazole (a dual inhibitor of CYP3A4 and CYP2C9, see also Section 5.1.5.4), the dose should be reduced to approximately 50% of the dose rounding to the nearest dosage strength. The concomitant use of ruxolitinib with fluconazole doses of greater than 200 mg daily should be avoided. More frequent monitoring of hematology parameters and clinical signs and symptoms of ruxolitinib related adverse reactions is recommended upon initiation of a strong CYP3A4 inhibitor. No dose adjustment is necessary when a mild or moderate CYP3A4 inhibitor is used concomitantly with ruxolitinib. No dose adjustment is necessary when a CYP3A4 inducer (such as, but not limited to, avasimibe, carbamazepine, phenobarbital, phenytoin, rifabutin, rifampin, rifampicin, St. John's) is used concomitantly with ruxolitinib. No dose adjustment is necessary when ruxolitinib is administered with a CYP3A4 substrate. Patients should be closely monitored and the ruxolitinib dose titrated based on safety and efficacy.

Women of child-bearing potential

Women of child-bearing potential must take appropriate precautions to avoid pregnancy during treatment. In case pregnancy occurs, risk-benefit evaluations must be carried out on an individual basis with careful counseling regarding potential risk to the fetus using the most recent data available.

Embryo-fetal development studies with ruxolitinib in rats and rabbits did not indicate teratogenicity. Ruxolitinib was embryotoxic and fetotoxic in rats (increases in post-implantation loss and reduced fetal weights). The potential risk for humans is unknown.

Breast-feeding

Women taking ruxolitinib should not breast-feed.

Overdosage

There is no known antidote for overdoses with ruxolitinib. Single doses up to 200 mg have been given with acceptable acute tolerability. Higher than recommended repeat doses are associated with increased myelosuppression including leukopenia, anemia and thrombocytopenia.

Appropriate supportive treatment should be given. Hemodialysis is not expected to enhance the elimination of ruxolitinib.

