23.3 Appendix C: Strong CYP3A4 and 2C8 Inhibitors and Inducers

| Strong Inhibitors | Strong Inducers |
|--|--|
| Protease Inhibitors: 
• Ritonavir• Indinavir• Nelfinavir | Anticonvulsants, mood stabilizers: 
• Phenytoin• Carbamazepine• Oxcarbazepine |
| Macrolide antibiotics: 
• Erythromycin• Telithromycin• Clarithromycin | Non-nucleoside reverse transcriptase inhibitors: 
• Efavirenz• Nevirapine• Etravirine |
| Azole antifungals: 
• Fluconazole• Ketoconazole• Itraconazole | Others: 
• Phenobarbital• Rifampicin• Modafinil• Hyperforin (constituent of St Johns Wort)• Cyproterone (antiandrogen, progestin) |
| Others: 
• Chloramphenicol• Nefazodone• Bergamottin (constituent of grapefruit juice)• Aprepitant• Verapamil• Gemfibrozil• Trimethoprim | |

Columbia University Medical Center
Herbert Irving Comprehensive Cancer Center
Version Date: 27 Jul 2023

| | |
|---|--|
| 
• Thiazolidinedione• Montelukast• Quercetin | |
|---|--|

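### Appendix C omits six strong CYP3A4 inhibitors named in Section 10.1, and the 50% dose cut gives a tie at 15 mg BID and, read per administration, no cut at 5 mg BID

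*Combined protocol and SAP*

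**What the plan says.** Section 6.2, exclusion 9, bars "Concurrent use of strong CYP3A4 or CYP3A4 substrate drugs with a narrow therapeutic range within 14 days or 5 drug half-lives" (whichever is longer) before study drug starts. No noun follows the first mention of CYP3A4. The criterion then says "A list of strong CYP3A4 and 2C8 inhibitors and inducers can be found in Appendix C", and the appendix carries the title "Strong CYP3A4 and 2C8 Inhibitors and Inducers".

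Section 10.1 has a paragraph on dose adjustment with CYP3A4 drugs. It gives an open-ended list of strong inhibitors and, when one is given with ruxolitinib, instructs that "the dose should be reduced to approximately 50% of the dose rounding to the nearest dosage strength". It requires no adjustment for inducers or for substrates. It also asks for closer blood-count monitoring when a strong inhibitor is started, and for titration of ruxolitinib on safety and efficacy.

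Section 8.1 tells sites: "Appropriate dose modifications for ruxolitinib are described in Section 9". Section 9 covers cycle-start laboratory criteria and reductions for toxicity, with four dose levels in Table 1: 15 mg BID, 10 mg BID, 5 mg BID and 5 mg once daily. Section 11.1 lists tablet strengths of 5, 10, 15, 20 and 25 mg, Section 11.6 describes 5 mg tablets, and Section 11.4 requires tablets to be swallowed whole.

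**The concern.** The first problem concerns eligibility. A site that checks exclusion 9 against Appendix C will not find six drugs that the same protocol treats as strong inhibitors, so a patient taking one of them could be admitted. The two azoles matter most. Appendix C has an azole antifungal group but leaves out posaconazole and voriconazole, in a trial of immunosuppressed transplant recipients for whom Section 10.1 itself warns of fungal infection.

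The second concerns dosing on treatment. The rounding instruction does not say whether the 50% applies to each administration or to the day's total, and it has no rule for a tie. Following it as written can give different doses at different sites at the starting dose planned in Section 5.1, and can leave the dose uncut at 5 mg BID. Section 10.1 says why over-exposure matters: "Higher than recommended repeat doses are associated with increased myelosuppression including leukopenia, anemia and thrombocytopenia".

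**Working it through.** No figure in the plan needs reproducing. The check is a comparison of two lists and a halving of each dose level.

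**Lists.** Setting fluconazole aside, because Section 10.1 names it separately, and counting nefazodone once (it is printed twice), Section 10.1 names 15 strong inhibitors. Appendix C lists 19 inhibitors.

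| Status in Appendix C | Drugs named in Section 10.1 | Count |
|---|---|---|
| Listed | clarithromycin, indinavir, itraconazole, ketoconazole, nefazodone, nelfinavir, ritonavir, telithromycin | 8 |
| Listed only as ritonavir | lopinavir/ritonavir | 1 |
| Absent | posaconazole, voriconazole, saquinavir, boceprevir, telaprevir, mibefradil | 6 |

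Check: 8 + 1 + 6 = 15. The number absent is seven if lopinavir/ritonavir is counted as an entry of its own.

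**Dose, read per administration.** Halve each dose and move to the closest strength in {5, 10, 15, 20, 25} mg. Using only 5 mg tablets in whole numbers gives the same results.

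- 15 mg BID: 15/2 = 7.5 mg. The distances are 7.5 − 5 = 2.5 and 10 − 7.5 = 2.5, a tie. The result is 5 mg BID (10/30 = 33% of the daily dose) or 10 mg BID (20/30 = 67%).
- 10 mg BID: 10/2 = 5 mg, so 5 mg BID (10/20 = 50%).
- 5 mg BID: 5/2 = 2.5 mg, and the closest strength is 5 mg, so 5 mg BID (10/10 = 100%, no cut).

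**Dose, read as a daily total in whole 5 mg tablets.**

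- 15 mg BID: 30/2 = 15 mg, given as 10 mg + 5 mg (50%).
- 10 mg BID: 20/2 = 10 mg, given as 5 mg BID (50%).
- 5 mg BID: 10/2 = 5 mg, given once daily (50%).

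The daily reading gives exactly half at each of these three levels.

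**The lowest level.** At 5 mg once daily, 5/2 = 2.5 mg, which is less than one tablet, so neither reading gives a cut. The footnotes to Tables 2 to 6 take a patient off therapy after more than two reductions. From 15 mg BID, two one-level reductions end at 5 mg BID. From 10 mg BID, two end at 5 mg once daily. Toxicity reductions therefore reach this level only from a 10 mg BID start.

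**The case against.** The protocol has real safeguards. Section 10.1 describes an approximate cut followed by closer blood-count monitoring and titration. Section 8.2 has the Principal Investigator alerted to any agent that may affect CYP3A4, and Section 9.2 sends unclear cases to the principal investigator or medical monitor. Exclusion 9 offers Appendix C as a list, not as the complete list, and the list in Section 10.1 is open-ended, so absence from the appendix is not permission. Exclusions 10 and 11 bar patients on combination antiretroviral therapy and patients whose hepatitis B or C needs antiviral treatment. They probably cover several of the six drugs, if those are such antivirals. At 15 mg BID every reading still lowers the dose. All of this stands and limits the size of the point. None of it supplies the missing azoles, breaks the 7.5 mg tie or produces a cut at 5 mg BID.

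The documents do not support some stronger readings that a reader might infer:

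- *That the fluconazole rules conflict.* Appendix C sets no dose threshold, while Section 10.1 says "The concomitant use of ruxolitinib with fluconazole doses of greater than 200 mg daily should be avoided". Each rule gives its own timing, however: exclusion 9 applies before study drug starts, and Section 10.1 applies while ruxolitinib is being given.
- *That exclusion 9 lets strong inhibitors through.* Its next sentence shows the intended words. The gap is clerical.
- *That the halving rule is missing from the protocol.* It has its own heading in Section 10.1. Its absence from Section 9 is a matter of placement. The reference in "a dual inhibitor of CYP3A4 and CYP2C9, see also Section 5.1.5.4" to a section this protocol lacks is also clerical.

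**Conclusion.** The point holds at minor severity. Appendix C omits six of the 15 strong inhibitors named in Section 10.1, on the view that ritonavir covers lopinavir/ritonavir. The halving rule allows 10 or 20 mg/day at 15 mg BID when read per administration, and 15 mg/day when read as a daily total. Read per administration, it makes no cut at 5 mg BID. Only the 10 mg BID level is free of doubt among the three levels that a patient starting at 15 mg BID can occupy under the toxicity rules.

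The weight given to the azoles rests on a drug-class assumption, that exclusions 10 and 11 catch several of the antivirals. The documents do not state this.

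A reader might go further and infer that patients will be harmed, or that the safety lead-in is compromised. The documents do not show that. They give no exposure ratio for strong inhibitors and no expected number of users, and the myelosuppression statement comes from the overdosage paragraph. Nothing here alters the sample size, the error rates or the efficacy analysis.

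**What to change.** 1. Add posaconazole, voriconazole, saquinavir, boceprevir, telaprevir and mibefradil to Appendix C, and mark it non-exhaustive.
2. Complete exclusion 9 as *strong CYP3A4 inhibitors or inducers*. The sponsor should confirm that inducers are meant, because Section 10.1 asks for no adjustment with them.
3. State that the 50% applies to the total daily dose, and put one dose per level in Section 9:

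| Current dose | Dose with a strong CYP3A4 inhibitor |
|---|---|
| 15 mg BID | 10 mg + 5 mg daily |
| 10 mg BID | 5 mg BID |
| 5 mg BID | 5 mg once daily |
| 5 mg once daily | avoid the strong inhibitor, or hold ruxolitinib |

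4. Align the sentence in Section 10.1 with this table, and remove the reference to the non-existent section in the same edit.

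The cost is amendment wording in exclusion 9, Section 9, Section 10.1 and Appendix C. It needs no new patients, visits or tests.
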